**Table 5. Power Analyses**

Time/Test	PN plus DVD (n=115 at 9 mos)	DVD only (n=115 at 9 mos)	Usual Care (n=115 at 9 mos)	Power
9 month/ Any Test	44%	20%	5%	.80-.99

group). By 12 months, the 150 in each intervention group will decrease to 115 through an approximate 25% attrition. The multivariable logistic regression models for the intervention effect on the CRC screening completion outcome while accounting for covariates will very likely have greater than 80% power, more than for the bivariate models because a smaller sample size is required when

covariates are added to the model. In addition, this sample size will most likely ensure greater than 80% power for other outcomes of Aim 1 (quality of bowel preparation, anxiety, and satisfaction) because they are continuous or ordinal variables. Specifically, the analysis of continuous outcomes using a general linear model will have 99% power to detect a

small effect size of .50 standard deviation units between outcome means, and the ordinal logistic regression models will have more information than the binary models.

For Aim 2, our main interest is in whether the intervention effects differ by age, race, gender, and income. We consider this aim to be exploratory as we do not have preliminary data to estimate the effect sizes; however, we feel it is important to explore interactions in this study as they may identify subgroups of patients who may not need the more intensive support of a PN. For Aim 3, the revised sample size of 115 per group will allow for the detection of mediation effects with 80% power assuming the effect sizes from the intervention to mediator and from the mediator to outcome are moderate or higher (which is what is typically assumed in a power calculation). For Aim 3, to test mediation effects, we will use the percentile bootstrap method to estimate the indirect/mediated effect. Simulations of the two-path mediation model in Mplus (Table 2) show that 115 subjects per group are needed to have 80% power to test the total indirect effect using the Sobel approach when the effect of the independent variable (the intervention variable here) on the mediator is small (.2) and independent variable on outcome is medium (.39). Using the percentile bootstrap method instead of Sobel should afford the same or greater power.

**C.13. Data Analyses. (IR-3, IR-5, MD-3, MD-5, HT-1, HT-2, HT-3, HT-4)** Preliminary analyses will compare baseline demographic information across groups using means and standard deviations for continuous variables and frequency distributions for categorical variables. We will adjust for those characteristics in subsequent analyses if significant differences emerge at a conservative level for inclusion of a covariate ( $p < .20$ ). Characteristics of participants who drop out by 9 months will be compared with those who remain to determine what biases may exist. **(MD-4)** The above analyses will be conducted using ANOVA, chi-square tests, or exact or non-parametric equivalents. If there appear to be biases in dropout, we will conduct pattern mixture models analyses to see how the results could change based on the MAR assumption **(IR-5, MD-2, MD-3, MD-5)**. Primary analysis of outcomes will employ an intent-to-treat analysis; all participants will be included regardless of compliance with interventions. The main outcome, CRC screening completion with any test (FIT or colonoscopy) will be extracted from medical records for all participants, including those who drop out or are lost to follow-up. Intervention exposure will be measured and its effects will be accounted for in the intent-to-treat analysis. First, we will know whether participants viewed none, part, or all of the DVD. Second, we will document how many contacts PNs make to or on behalf of participants assigned to that group. These variables (viewed none/part/ or all of the DVD and number of navigator contacts) will be added as covariates in analyses. For all aims, sensitivity analysis will be conducted as needed for each outcome to assess the effects of the model assumptions on the results **(IR-5)**. Assumptions, such as normality of residuals, will be checked and appropriate modifications to the analysis plan applied if needed, such as transformations or use of non-parametric methods. From our prior studies, we expect missing data to be minimal (less than 2%) for subjects during participation. For missing data on scales, we will use mean imputation as long as two-thirds of the questions have been answered (or per validated instrument instructions, if otherwise). **(MD-2, MD-3)**

For Aim 1, we will test the primary hypothesis related to comparing intervention effects among the three randomized groups (H1.1: PN+DVD vs. DVD only and H1.2: PN+DVD vs. usual care and DVD only vs. usual care) using the outcome of completion of CRC screening using any test at 12 months post-baseline. In addition, quality of bowel preparation, procedural anxiety, and satisfaction with the screening experience will be examined as outcomes. As an initial assessment of CRC screening completion at 12 months, we will use a chi-square test for a 3 x 2 (group by screening completion) contingency table to test whether completion rates differ across groups. If the  $p$ -value for the overall test is significant at the .05 level, pair-wise 2 x 2 tests will be conducted at the  $.05/3 = .017$  level. However, the primary analyses for Aim 1 will involve fitting multivariable logistic regression models of the primary outcome of 12-month CRC screening test completion (yes/no). Independent variables will be group assignment and continuous and categorical individual characteristics. These models will also allow us to investigate intervention effects on CRC screening test completion while adjusting for potential confounders. Group assignment will be coded using dummy variables with usual care as the reference category. For H1.3, quality of bowel preparation will be analyzed for those participants who complete colonoscopy with proportional-odds ordinal logistic regression using an ordinal dependent variable ( $1 = \text{excellent}$ ,  $2 = \text{good}$ ,  $3 = \text{fair}$ ,  $4 = \text{poor}$ ,  $5 = \text{inadequate}$ ). If some outcome categories are sparse, the outcome will be dichotomized into adequate

(*excellent or good*) versus inadequate (*fair, poor, or inadequate*). The outcomes of anxiety and satisfaction are continuous outcomes and will be modeled with linear regression.

**Aim 2. Examine age, race/ethnicity, sex and income as potential moderators of intervention effects. (RQ-4, HT-1, HT-2, HT-3, HT-4)** We will fit multivariable models as in Aim 1, except now including interaction terms for age (< 65, age 65+), race/ethnicity (Non-hispanic Black, Non-hispanic White), sex (male, female), and annual income (<\$15,000, ≥\$15,000), respectively. Moderators will be identified by significant interaction terms in regression models. The key moderation effects of interest will be between PN+DVD vs. DVD only. Moderation of PN+DVD vs. usual care, and DVD only vs. usual care also will be examined. Hispanics will be excluded from race/ethnicity interaction tests due to small sample sizes.

**Aim 3. Examine changes in knowledge and health beliefs (knowledge, perceived risk, perceived benefits, barriers, and self-efficacy) as potential mediators of intervention effects. (RQ-6)** Mediation analysis will be conducted to identify potential mediators. Specifically, for each of the variables (changes in knowledge, perceived risk, perceived benefits, perceived barriers, and self-efficacy) mediation effects will be estimated in an logistic regression setting, fitting the appropriate mediation models using MPlus and then testing indirect effects using the percentile bootstrap approach to estimate the indirect effect. We will fit models that estimate the effects of PN plus DVD vs usual care and DVD only vs usual care, and also models that compare the strength of the indirect effects between the PN plus DVD and DVD only arms. We expect to see a difference in mediation effects mainly on barriers, with the PN plus DVD having a greater mediation effect on barriers than DVD only.

**C.14. Potential problems, strategies and benchmarks for success.** Potential problems are described below along with plans to minimize them. (*IR-6, MD-1, MD-2, MD-4*)

- *Loss to follow-up:* It is anticipated that there will be some loss to follow-up because of participant dropout, death, or relocation. Based attrition data through May 31,2019 , we estimate the loss to be approximately 25% over the 9-month study period, which has been accounted for in the revised power analysis and sample size determination.
- *Limited internal validity:* Randomization will minimize the influence of extraneous variables on outcomes.
- *Missing data:* Missing data will be minimized through the use of telephone data collection methods and through interviewer training. All characteristics at baseline will be examined to determine potential bias that would require subsequent caution regarding interpretation of results.
- *Limited generalizability:* We will recruit participants from one safety net system who will be predominantly low-income, which limits generalizability. However, we will compare outcomes for a racially diverse group of low-income patients and explore whether age, sex, or race/ethnicity moderate the effects of the two interventions. (*RQ-4, IR-6*)
- *Sample bias:* Based on our preliminary studies, we estimate that approximately 55% of eligible people who are contacted will be willing to participate. It is possible that those who are motivated to complete CRC screening will self-select into the study. To examine the representativeness of our sample, we will compare demographic characteristics of those who agree to participate with those who do not. (*PC-2, IR-6*)

**C.15. Impact:** At the completion of this study, we will have developed two theory-based and highly translatable and easy to disseminate interventions to promote CRC screening and improve quality of bowel preparation for those who undergo colonoscopy. These interventions will be designed to be flexible and modifiable as science advances and as the needs of individual patients and health care systems change. Interventions that are easily modified to meet the needs of diverse populations and settings that counsel patients about the need for CRC screening, support them to complete screening in a timely manner, and assist those who undergo colonoscopy to properly prepare (cleanse their bowel) for the procedure are urgently needed. Knowledge of the comparative effectiveness of these interventions will inform the next steps required for translation of interventions into clinical practice.

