**C. Study Design and Approach. (RQ-2, RQ-3, RQ-4, RQ-5, RQ-6)**

We will use a three-group randomized trial design to compare the effectiveness of two theory-based interventions to promote completion of CRC screening among individuals at average risk for CRC and, for those who complete colonoscopy, high quality bowel preparation. We will enroll an ethnically diverse group of 450 men and women who canceled, or did not attend, their colonoscopy appointment and randomize them to receive: 1) a tailored DVD intervention; 2) the tailored DVD *plus* a patient navigator intervention; or 3) usual care. The aims of this study are to:

**1. Compare the effectiveness of two interventions designed to promote CRC screening among people at average risk for CRC - a tailored DVD versus the tailored DVD *plus* telephone-based patient navigation - to each other and to usual care.**

Hypothesis 1.1: Participants who receive the tailored DVD *plus* telephone-based patient navigation intervention will have higher rates of colorectal cancer screening with fecal immunochemical test (FIT), colonoscopy, or either screening test compared to those who receive the tailored DVD alone.

Hypothesis 1.2: Participants who receive either intervention will have higher rates of colorectal cancer screening with fecal immunochemical tests (FIT), colonoscopy, or either screening test than those who receive usual care.

[figure not shown]
Hypothesis 1.3: Participants who receive either intervention who complete colonoscopy will have: 1) better quality of bowel preparation; 2) less anxiety about the procedure; and 3) greater satisfaction with the colonoscopy experience than those who receive usual care.

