The DVD process interview will assess receipt of, viewing of, and satisfaction with the DVD and will be done approximately 2 weeks post-mailing of the DVD. Receipt, experience and satisfaction with the PN intervention, for those randomized to the DVD+PN group, will be assessed as part of the 6 month interview (T2). The 6 month interview will also assess changes in knowledge, patient activation, CRC fear, cancer fatalism, and colonoscopy-related procedural anxiety. Health beliefs for colonoscopy and FIT will be assessed as will self-reported CRC screening intention, uptake and satisfaction with the screening experience (for those who completed screening). At 9 months, we will assess self-reported CRC screening intention, uptake and satisfaction with the screening experience (for those who completed screening since T2). Participants will receive a \$50 gift card for the baseline interview, a \$50 gift card for the 6 month interview and a \$50 gift for completing the 9 month interview; a total of \$150 for participants who complete all three interviews. Participants who complete the additional DVD process interview will receive another \$50 gift card for a total of \$200 in gift cards. By using gift cards with an appealing dollar amount over the 9 month data collection period, we hope to incentivize participants to remain in the study. Additional retention strategies which we will use include mailing

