**Table 3: Data Collection Timeline**

Measures	Baseline Interview (T1)	Process Interview (2 weeks after mailing DVD)	Follow-up Interview at 6 months post-baseline (T2)	Final Interview at 9 months post-baseline (T3)	12 months post-baseline (Final medical record review)
Demographics, social support, media exposure	X				
Health literacy, health status to include co-morbidities	X				
CRC screening experience and readiness to screen, patient activation, health beliefs (perceived CRC risk, benefits of screening, barriers to screening, self-efficacy for screening), CRC fear, cancer fatalism	X		X		
Colonoscopy-related procedural anxiety	X		X	X	
CRC and screening knowledge	X		X		
Receipt, viewing and satisfaction with the DVD		X			
Receipt, experience & satisfaction with the PN			X		
Self-report of CRC screening intention and completion			X	X	
Satisfaction with the screening experience			X	X	
Trial participation feedback				X	
Medical record review: CRC screening test completion, quality of bowel preparation			X	X	X

**C.9. Measures.** The primary study outcomes of CRC screening completion with any test (FIT or colonoscopy), and quality of bowel preparation (for those who complete colonoscopy), colonoscopy-related procedural anxiety and satisfaction with the CRC screening experience are described in this section. Secondary outcomes of the interventions include changes in knowledge and health belief variables (perceived risk, benefits, barriers, and self-efficacy). Other measures include patient activation, CRC fear, cancer fatalism, and satisfaction with the interventions. Measures have been extensively tested and refined in preliminary studies, and are described in more detail elsewhere.

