**PRIMARY OUTCOME MEASURES: (RQ-6, PC-2, IR-4)**

**Completion of any CRC screening test** (fecal immunochemical test (FIT) or colonoscopy) will be measured by medical record review. FIT and colonoscopy completion dates will be extracted from the electronic medical record. Because self-report of CRC screening has correlated well with medical record data, we will also use validated items from our previous research to ask participants if they have had a CRC screening test (FIT or colonoscopy) as well as their plan to have one in the next 6 months (only for those who have not yet completed screening).

**Quality of bowel preparation** will be assessed two ways for those participants who attend their colonoscopy: 1) by participant self-report of their bowel prep experience and 2) via review of electronic medical records. When patients arrive in the endoscopy department, a nurse assesses their experience with the bowel preparation and adherence to dietary restrictions. Patients who report they were unable to complete the bowel prep or have eaten in the past 24 hours are considered inadequately prepped for the procedure and sent home. These patients must repeat the preparation to cleanse the bowel and reschedule their colonoscopy. For those who report successful completion of the bowel prep and adherence to dietary restrictions, quality of the bowel preparation (i.e. degree of cleanliness/emptiness of the bowel) is evaluated by the endoscopist during the colonoscopy. Standard practice is to evaluate bowel preparation quality using an assessment similar to the Aronchick 5-point scale where 1=*excellent*, 2=*good*, 3=*fair*, 4=*poor*, and 5=*inadequate*. Adequate is a term that may also be used to describe the quality of bowel preparation as a single descriptor or in addition to the Aronchick assessment as excellent (1), good (2), or fair (3). Procedural notes including endoscopists' ratings of the quality of the bowel prep are entered into ProVation, a menu-driven software program. Therefore, participants will be considered inadequately prepped if they are: 1) deemed inadequately prepped from self-report during initial nursing assessment OR 2) if the endoscopist rates the quality of the bowel prep as poor (4)

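### Section C.12 bases power for bowel preparation and satisfaction on whole arms of 115, but only completers contribute; for satisfaction, power for 0.50 SD against usual care is 18–21% at the planned rates

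*Combined protocol and SAP*

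**What the plan says.** Section C.12 sizes the trial on any-test screening completion: 115 analysed per arm, with assumed rates of 44% (PN+DVD), 20% (DVD only) and 5% (usual care). It then extends the result: "this sample size will most likely ensure greater than 80% power for other outcomes of Aim 1 (quality of bowel preparation, anxiety, and satisfaction"). The reason given is that these outcomes are continuous or ordinal. It adds that "the analysis of continuous outcomes using a general linear model will have 99% power to detect a" difference of 0.50 SD. No reduction is made for who supplies data.

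Other sections restrict who does:

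- Hypothesis 1.3 (Section C): "Participants who receive either intervention who complete colonoscopy will have: 1) better quality of bowel preparation; 2) less anxiety about the procedure", and "greater satisfaction with the colonoscopy experience than those who receive usual care".
- Section C.8, on the follow-up interviews: "uptake and satisfaction with the screening experience (for those who completed screening").
- Section C.13 models bowel preparation in colonoscopy completers by proportional-odds regression. Anxiety and satisfaction are modelled by linear regression, with no population stated.
- Section C.9 gives these outcomes primary standing: "The primary study outcomes of CRC screening completion with any test (FIT or colonoscopy), and quality of bowel preparation (for those who complete colonoscopy"), followed by procedural anxiety and satisfaction.

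**The concern.** The power statement uses a denominator that two of its three outcomes cannot have. If 5% of usual-care participants complete screening, about six people represent that arm in every comparison of satisfaction or bowel preparation with usual care. An ordinal or continuous scale does not make up for that.

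Readers of a null result on Hypothesis 1.3 would take it that the trial had 80–99% power and conclude that the interventions do not improve preparation or satisfaction. With so few usual-care completers, a non-significant result would say little about the 0.50 SD that C.12 names.

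**Working it through.** **Inputs.** 115 analysed of 150 randomised per arm, and rates of 44/20/5% (C.12). Effect 0.50 SD (C.12). Attrition of about 25% at the 6-month interview (E.1). An alternative usual-care rate of 18%, from the team's earlier trial in the same health system (B.1). The documents set .0167 (.05/3) for the pairwise screening tests and no level for Hypothesis 1.3, so both .05 and .0167 are shown, two-sided. The rates are for any test, so they are an upper bound for colonoscopy.

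**Formula for continuous outcomes.** Two-sample t test with noncentrality δ = 0.5 × √(n₁n₀/(n₁+n₀)) and n₁+n₀−2 degrees of freedom.

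**Step 1: the plan's figure.**
- 115 vs 115: δ = 0.5 × √57.5 = 3.79. Power is 96.5% at .05 and 91.5% at .0167.
- Both interventions pooled, 230 vs 115: δ = 0.5 × √76.7 = 4.38. Power is 99.2% at .05.

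So a figure near 99% is obtained only when whole arms are counted.

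**Step 2: expected completers per 115.** 115 × 0.44 = 50.6; 115 × 0.20 = 23; 115 × 0.05 = 5.75. Pooled interventions: 73.6. Satisfaction comes from the interviews, where attrition applies, so 115 is its base.

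**Step 3: satisfaction, 0.50 SD, against usual care.** At the planned rates:
- PN+DVD: δ = 0.5 × √(50.6 × 5.75/56.35) = 1.14
- DVD: δ = 0.5 × √(23 × 5.75/28.75) = 1.07
- Pooled: δ = 0.5 × √(73.6 × 5.75/79.35) = 1.15

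Each cell below is in the order PN+DVD / DVD / pooled.

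| Usual-care rate (completers) | Power, .05 | Power, .0167 | Detectable with 80% power, .05 |
|---|---|---|---|
| 5% (5.75) | 20 / 18 / 21% | 10 / 8 / 10% | 1.26 / 1.36 / 1.23 SD |
| 10% (11.5) | 32 / 27 / 34% | 18 / 14 / 20% | 0.93 / 1.04 / 0.90 SD |
| 18% (20.7) | 47 / 36 / 51% | 30 / 21 / 34% | 0.74 / 0.87 / 0.70 SD |

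If only 75% of screeners had colonoscopy (an assumption), the .05 figures fall to 14–17% at a 5% usual-care rate and 28–40% at 18%.

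For 80% power at .05, usual-care completion would have to reach about 49% for the pooled contrast or 75% for PN+DVD. DVD versus usual care cannot get there: 23 DVD completers against all 115 usual-care participants gives 58%.

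**Step 4: bowel preparation.** C.13 says screening completion is taken from medical records for everyone, including dropouts. If bowel preparation is too, the base could be 150 per arm: 66, 30 and 7.5 completers. C.12 names no ordinal effect, so odds ratios of 2 and 2.5 are assumed. Three usual-care distributions over the five categories are also assumed: 10/40/25/15/10, 20/40/15/15/10 and 10/30/30/20/10%. The test is a tie-corrected rank-sum test (the score test of the two-group proportional-odds model) at .05, with 20,000 simulated trials per case. Ranges cover the three contrasts, the three distributions and 115–150 per arm.

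| Usual-care rate | OR 2 | OR 2.5 |
|---|---|---|
| 5% (6–8 completers) | 12–18% | 18–28% |
| 18% (21–27 completers) | 23–42% | 35–64% |
| Whole arms, 115 vs 115 | 81–83% | 96–97% |

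A fitted proportional-odds likelihood-ratio test (first distribution, 1,500 replicates) gives similar values. For OR 2 and 2.5, 51 vs 6 gives 16% and 22%, and 66 vs 27 gives 41% and 59%.

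**Step 5: anxiety.** Hypothesis 1.3 words it for completers, Table 3 collects it with no such limit, and C.13 sets none. On whole arms its power is that of Step 1, so the claim above 80% holds. In completers it would fail as satisfaction does.

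**The case against.** - **Standing of the outcomes.** C.12 is hedged and sizes the trial on screening completion. C.13 treats the Hypothesis 1.3 outcomes as additional. The labels are mixed: C.9's opening calls all of them primary, but its primary-measures part describes only screening completion and bowel preparation, and anxiety is described under secondary measures. This limits the consequence. It does not rescue the figures, and the 99% sentence carries no hedge.
- **Bowel-preparation effects.** The distributions and odds ratios are assumed, so those power values are conditional. This stands. The results barely move across the three distributions, and the same effects give over 80% on whole arms.
- **Who counts as a completer.** C.9 says: "Patients who report they were unable to complete the bowel prep or have eaten in the past 24 hours are considered inadequately prepped", and they are sent home. If they are analysed, the set is larger than the completers. The documents give no count. Section A puts inadequate cleansing at 25–30% of those presenting. Taking all of 30% as sent home would raise the usual-care count only to 5.75/0.70 = 8.2, or 7.5/0.70 = 10.7 on 150 per arm, well below the 21–27 of the 18% case.
- **Choice of 18%.** It is a 6-month rate in a different group of patients, and the usual-care/non-tailored column of Table 1 reaches 32.6%. At that rate satisfaction power is 46–70% at .05, still below 80%. So 36–51% illustrates one rate and is not an outer limit.
- **Pooling.** C.13 codes two separate dummy variables and writes no pooled contrast. Without pooling, the ranges are 18–20% and 36–47%. The pooled values are the favourable reading of Hypothesis 1.3.

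**Conclusion.** The concern holds. The power stated for satisfaction and bowel preparation is wrong as written, because it counts people who cannot contribute data. For satisfaction the conclusion rests on the plan's own rates, its 0.50 SD and a two-sided .05 level, which is the lenient choice: power is 18–21% where above 80% and 99% are stated. No usual-care rate considered, from 5% to 32.6%, brings it to 80%. For bowel preparation the direction is equally clear, but the size depends on assumed effects. For anxiety the claim depends on a population that the plan leaves open. Sample size and the main screening comparison are unaffected. This should be corrected before the Hypothesis 1.3 results are interpreted.

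**What to change.** 1. In C.12, replace the above-80% and 99% statements for bowel preparation and satisfaction with power or detectable differences at the expected number of completers. Show usual-care rates of 5–18%, with 115 per arm for satisfaction and 115–150 for bowel preparation, and state the significance level.
2. Label the completer-only comparisons with usual care as descriptive and low-powered. This lowers the standing that C.9 gives them, so the two sections should be made to agree.
3. State the analysis population and follow-up time for anxiety. The text of C.8 lists it at 6 months only, Table 3 at 6 and 9 months. Keep the above-80% statement only if all participants are analysed.
4. Before any binary analysis of bowel preparation, reconcile C.9 with C.13. C.9 allows the term adequate "in addition to the Aronchick assessment as excellent (1), good (2), or fair (3"), and counts only the two worst ratings as inadequate; C.13 puts *fair* on the inadequate side. Also state whether attendees who are sent home are included.

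The cost is revised wording and less favourable stated figures. No new data, endpoint or participants are needed.
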